### **2.6.3 Handling of missing values/censoring/discontinuations**

Missing data handling of secondary analyses for different endpoints are specified in [Section 2.6.2](#).

## **2.7 Safety analyses**

For all safety analyses, the FAS will be used. All listings and tables will be presented by the treatment group.

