## 2      Statistical methods

### 2.1      Data analysis general information

The analyses will be performed by the Contract Research Organization (CRO) using SAS 9.4.

Categorical data will be presented as frequencies and percentages. For continuous data, mean, standard deviation, median, minimum, and maximum will be presented. These summary statistics will be presented by the treatment group unless otherwise specified. Where appropriate, point estimates and confidence intervals (CI) of treatment group differences will be provided.

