#### 2.1.1      General definitions

##### 2.1.1.1      Study treatment

The following treatment groups will be presented:

- Untreated control
- Low dose GT005 (████ vg)
- High dose GT005 (████ vg)

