### 2.1.1.2 Baseline and post-Baseline

*Baseline* (Day 1) is defined as

- the day following randomization for subjects randomized to untreated control
- the day of successfully receiving GT005 administration for subjects randomized to GT005
- or the latest surgery date for subjects who were randomized to GT005 but failed to receive GT005 administration on the first attempt to surgery (if applicable)

The baseline value for efficacy and safety variables is the last available value (scheduled or unscheduled) collected prior to the date of *Baseline*, or on the date of *Baseline* but prior to the time of GT005 administration for GT005 treatment groups.

All data collected after the date of *Baseline* are defined as post-baseline. The *study day* for a baseline or post-baseline scheduled or unscheduled visit is defined as:

$$\text{Study day} = \begin{cases} (\text{Date of visit}) - (\text{Date of randomization}) & \text{Untreated} \\ (\text{Date of visit}) - (\text{Date of treatment administration}) + 1 & \text{GT005} \end{cases}$$

The *study day* for a scheduled or unscheduled visit before baseline is defined as

$$\text{Study day} = \begin{cases} (\text{Date of visit}) - (\text{Date of randomization}) - 1 & \text{Untreated} \\ (\text{Date of visit}) - (\text{Date of treatment administration}) & \text{GT005} \end{cases}$$

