## **2.2 Analysis sets**

The **All-Enrolled Set** includes all patients who signed informed consent. This analysis set will be used to summarize subject disposition.

The **Full Analysis Set (FAS)** will include all subjects who are randomized to GT005 or untreated control. The FAS will be used for the analysis of efficacy and safety data.

The number and percentage of subjects within each of the above analysis sets will be summarized.

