### 2.6.2 Statistical hypothesis, model, and method of analysis

1. Change from baseline through Week 96 in GA area as measured by FAF
  - MMRM as described in [Section 2.5.2](#) will be applied to the change from baseline through Week 96 in GA area, with intercurrent events and missing data handled in the same way as for the primary estimand ([Section 2.5.3](#)).

The estimated least-squares mean (LSM) for the change in GA area, and treatment difference against untreated control, as well as the corresponding 90% confidence interval, will be summarized by visit and treatment groups. A line plot for the estimated LSM with 90% CI by visit and treatment groups will also be provided. All assessments of GA area will be listed by treatment group, site, and subject.

2. Frequency of treatment emergent adverse event (AE) through Week 96

- The summary tables for treatment-emergent serious AE (TESAE) will be presented as described in [Section 2.7.1](#).
- Subjects who did not receive treatment due to surgical procedure related AEs will be listed separately by treatment group.

3. Change in retinal morphology on multimodal imaging through Week 96

- The presence of the following retinal morphology will be summarized based on observed data by visit for the number and percentage of subjects in reported categories:
  - i. Junctional zone of GA (Increased FAF, Normal FAF, Not Applicable, Cannot Grade) assessed by FAF.
  - ii. Junctional zone patterns (Atypical, Banded, Diffuse, Focal, Cannot Grade) assessed by FAF.

4.a Change in best corrected visual acuity (BCVA) Score via the early treatment for diabetic retinopathy (ETDRS) chart through Week 96

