### **2.7.1 Adverse events (AEs)**

Only AEs that occurred during the study period (from the date of randomization to the end of study) will be summarized. AEs recorded after screening but before the date of randomization will be listed only.

**Treatment-emergent Adverse Event (TEAE):** An adverse event is considered treatment emergent if the start date/time of the event is on or after the date of randomization, irrespective of the treatment arm. The primary summaries of AEs will be based on TEAEs.

The number (and percentage) of subjects with AEs will be summarized separately for ocular (study eye and fellow eye) and non-ocular events by treatment group in the following ways unless otherwise specified:

- Overall summary of death, subjects with any AE, any severe AE, any study treatment-related AE, any surgical procedure related AE, any AE leading to study discontinuation, any serious AE (SAE), any study treatment-related SAE, any surgical procedure related SAE, any SAE leading to study discontinuation
- AEs by primary SOC and PT
- AEs related to study treatment by SOC and PT (separately for study eye and non-ocular)
- AEs related to surgical procedure by SOC and PT (separately for study eye and non-ocular)
- SAEs by primary SOC and PT

- SAEs related to study treatment by SOC and PT (separately for study eye and non-ocular)
- SAEs related to surgical procedure by SOC and PT (separately for study eye and non-ocular)

A subject with multiple adverse events within a primary SOC is only counted once towards the total of the primary SOC.

All AEs, deaths, and SAEs (including those from the pre- and post-treatment periods) will be listed and those collected after the use of alternative GA therapies/medications, or during the pre-treatment, post-study period will be flagged. In addition, subjects who are not receiving treatment due to surgical procedure-related AEs will be listed separately by treatment group.

The MedDRA version used for reporting the AEs will be described in footnote.

For the legal requirements of ClinicalTrials.gov and EudraCT, two required tables on “on-treatment/treatment emergent” adverse events which are not serious adverse events with an incidence greater than 2% (or other cutting point as appropriate) and on “on-treatment/treatment emergent” serious adverse events and SAE suspected to be related to study treatment will be provided by system organ class and preferred term on the safety set population (i.e., the FAS of this study).

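### Vector-related and procedure-related AE percentages are planned on everyone randomised, by a treatment group that the SAP does not define as allocated or received

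*SAP*

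**What the plan says.** **Population.** SAP 2.7 says "For all safety analyses, the FAS will be used". SAP 2.2 defines that set: it "will include all subjects who are randomized to GT005 or untreated control". Table 5-1 excludes only subjects who were not randomised. For the registry AE tables, SAP 2.7.1 works "on the safety set population (i.e., the FAS of this study").

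**Grouping.** SAP 2.1 sets the default: "These summary statistics will be presented by the treatment group unless otherwise specified". SAP 2.1.1.1 begins "The following treatment groups will be presented" and names untreated control, low dose and high dose. It does not say whether a subject's group is the one allocated or the one received, and no other SAP section does.

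**Affected tables.** SAP 2.7.1 plans percentages of subjects with AEs and SAEs attributed to study treatment and, separately, to the surgical procedure. SAP 2.7.1.1 does the same for AESIs.

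**Protocol rule.** Protocol 9.4.3 and the synopsis display systemic AEs by treatment received and ocular AEs by allocation. SAP section 4 records that the protocol's Safety Analysis Set was dropped. It has no entry on this grouping rule.

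**Undosed subjects are foreseen.** Protocol 4.3 offers subjects randomised to GT005 but not dosed the option of staying in the study on the control visit schedule. SAP 2.4.1 counts subjects who left before surgery and those whose surgery was not completed successfully. SAP 2.1.1.2 has a baseline rule "for subjects who were randomized to GT005 but failed to receive GT005 administration on the first attempt to surgery".

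**The concern.** An undosed subject cannot have an event caused by the vector, and a never-operated subject cannot have one caused by the surgery. Keeping such people in the denominator lowers the percentage without adding any information about risk. For a one-time subretinal gene therapy whose safety and tolerability is a secondary objective, the useful figure is the risk per person dosed or per person operated on.

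The missing grouping rule adds a second problem. Two programmers could follow this SAP correctly and place the same undosed subject in different columns.

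**Working it through.** The plan gives no figure to reproduce, since the issue is a denominator and a grouping rule. The check takes each possible reading in turn.

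**Which reading does the SAP suggest?** SAP 2.6.2 says "Subjects who did not receive treatment due to surgical procedure related AEs will be listed separately by treatment group", and SAP 2.7.1 repeats that "subjects who are not receiving treatment due to surgical procedure-related AEs will be listed separately by treatment group". If the group were the treatment received, all these subjects would be untreated and splitting the listing by group would have no purpose. That points to allocation. The protocol's rule for systemic events points to treatment received. Neither is stated in the SAP.

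**Reading 1: by allocation.** Let q be the share of a dose group that was undosed (for vector-related events) or never operated on (for procedure-related events). Nobody in that share can have the event, so

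reported % = true % among the exposed × (1 − q).

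The documents do not give q. Assuming a range of 0 to 10%, a true 20% is reported as follows:

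| q | Reported |
|---|---|
| 0 | 20.0% |
| 2% | 19.6% |
| 5% | 19.0% |
| 10% | 18.0% |

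*Planned group sizes.* SAP section 3 gives about 202 in total and about 10 in high dose; SAP 1.1 gives 2:1 allocation. The low-dose size has to be inferred:
- 2:1 applied to the rest: (202 − 10) × 2/3 = 128.
- 2:1 applied to everyone: 202 × 2/3 ≈ 135 on GT005, less 10 high dose = 125.

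*Effect of one undosed subject, in relative terms.* Low dose: 1/128 = 0.78% to 1/125 = 0.80%. High dose: 1/10 = 10%.

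*Hypothetical counts.*
- Low dose, 5 of 125 undosed: 24/120 = 20.0% becomes 24/125 = 19.2%.
- High dose, 1 of 10 undosed: 2/9 = 22.2% becomes 2/10 = 20.0%.

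**Reading 2: by treatment received, in the three planned columns.** A subject operated on without receiving vector has no column except untreated control, so surgical AEs would appear there. With 128 low dose and 64 control, three undosed low-dose subjects would move the denominators to 125 and 67. If one of the three had a procedure-related AE, untreated control would show 1/67 = 1.5%, although nobody allocated to that arm has surgery.

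**Which q applies to which table.** A subject operated on but not dosed was exposed to the surgery and belongs in the procedure-related denominator. Only never-operated subjects dilute that one. All undosed subjects dilute the vector-related one.

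**The case against.** The strongest reply is that a rule exists. The SAP is based on protocol V6.0 and says that it covers what is planned in, or changed from, that protocol. Section 4 lists no change to the 9.4.3 display, so the protocol rule can fairly be read as still in force, and systemic events would then not be diluted. This stands. A reader might infer that the SAP silently abandoned the protocol rule; the documents do not show that. They show a rule neither repeated nor revoked, and SAP listings that fit allocation better.

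Other points on that side:

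- **Ocular events.** The protocol itself groups these by allocation, so any dilution there is inherited and is not a SAP error. That is fair, but the main surgical risks described in protocol 1.6.1.2 are ocular, so this is where the denominator matters most.
- **Removal of the Safety Analysis Set.** It is tempting to blame this. The protocol's set required randomisation and one post-baseline observation, not dosing, so its removal did not cause the problem.
- **Evidence of undosed subjects.** SAP 2.1.1.2 concerns a failed first attempt, and protocol 6.1.3.2 lets a deferred administration be rescheduled. Such subjects may be dosed later. Protocol 4.3 and SAP 2.4.1 are the better evidence that undosed subjects are foreseen. No document says that there were any.
- **Re-division by hand.** SAP 2.3.1 and 2.4.1 report how many were operated on and treated, so a reader can recompute the related-event percentages. This lowers the stakes but leaves the printed percentages as they are.
- **Context.** The study is exploratory, no inferential testing is planned, and development has stopped. No decision rule depends on these percentages.

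A reader might also infer that every safety percentage is too low. That does not follow. Undosed subjects can have all-cause AEs, BCVA loss and abnormal laboratory values, so no direction can be claimed for those outputs.

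**Conclusion.** The point holds in a limited form. All safety outputs run on everyone randomised, the SAP does not define the grouping, and the protocol's split rule is left unreconciled. Under allocation, vector-related and procedure-related percentages are understated by exactly the undosed or never-operated share. Under treatment received, surgical AEs of undosed subjects can land in untreated control. Dilution is therefore conditional on the reading, except for ocular events if the protocol rule is followed.

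The size is unknown and may be zero. At an assumed share of 2 to 5%, a true 20% loses 0.4 to 1.0 percentage points. The high-dose group is the sensitive one, because one subject there is a tenth of the denominator. These sizes rest on planned numbers; the study was terminated early, so actual groups may be smaller. This is a worthwhile, inexpensive improvement and does not invalidate the safety analysis.

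**What to change.** In SAP 2.7:

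1. State whether treatment group means allocated or received, separately for ocular and non-ocular events if they differ. Reconcile this with protocol 9.4.3 and record any change in section 4.
2. For AEs, SAEs and AESIs related to study treatment, use subjects who received GT005, by dose received, as the denominator.
3. For those related to the surgical procedure, use all subjects who underwent study surgery. Keep subjects operated on without vector in their allocated dose column; do not merge them with untreated control.
4. Keep the all-cause AE tables and the registry tables on the FAS by allocation, so that no SAE of an undosed subject is lost. Show the numbers dosed and operated on in the column headers.

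No change is needed to the BCVA-loss or laboratory outputs.

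The cost is some SAP wording, a derived exposure variable and a few extra tables; SAP 2.4.1 already lists the surgical and dosing records. There are two downsides. High-dose denominators are small, and columns of dosed subjects beside untreated control are not a randomised comparison and should be footnoted as such.

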### **2.7.1 Adverse events (AEs)**

Only AEs that occurred during the study period (from the date of randomization to the end of study) will be summarized. AEs recorded after screening but before the date of randomization will be listed only.

**Treatment-emergent Adverse Event (TEAE):** An adverse event is considered treatment emergent if the start date/time of the event is on or after the date of randomization, irrespective of the treatment arm. The primary summaries of AEs will be based on TEAEs.

The number (and percentage) of subjects with AEs will be summarized separately for ocular (study eye and fellow eye) and non-ocular events by treatment group in the following ways unless otherwise specified:

- Overall summary of death, subjects with any AE, any severe AE, any study treatment-related AE, any surgical procedure related AE, any AE leading to study discontinuation, any serious AE (SAE), any study treatment-related SAE, any surgical procedure related SAE, any SAE leading to study discontinuation
- AEs by primary SOC and PT
- AEs related to study treatment by SOC and PT (separately for study eye and non-ocular)
- AEs related to surgical procedure by SOC and PT (separately for study eye and non-ocular)
- SAEs by primary SOC and PT

- SAEs related to study treatment by SOC and PT (separately for study eye and non-ocular)
- SAEs related to surgical procedure by SOC and PT (separately for study eye and non-ocular)

A subject with multiple adverse events within a primary SOC is only counted once towards the total of the primary SOC.

All AEs, deaths, and SAEs (including those from the pre- and post-treatment periods) will be listed and those collected after the use of alternative GA therapies/medications, or during the pre-treatment, post-study period will be flagged. In addition, subjects who are not receiving treatment due to surgical procedure-related AEs will be listed separately by treatment group.

The MedDRA version used for reporting the AEs will be described in footnote.

For the legal requirements of ClinicalTrials.gov and EudraCT, two required tables on “on-treatment/treatment emergent” adverse events which are not serious adverse events with an incidence greater than 2% (or other cutting point as appropriate) and on “on-treatment/treatment emergent” serious adverse events and SAE suspected to be related to study treatment will be provided by system organ class and preferred term on the safety set population (i.e., the FAS of this study).

If for the same subject, several consecutive AEs (irrespective of study treatment causality, seriousness and severity) occurred with the same SOC and PT:

[figure not shown]
- a single occurrence will be counted if there is  $\leq 1$  day gap between the end date of the preceding AE and the start date of the consecutive AE
- more than one occurrence will be counted if there is  $> 1$  day gap between the end date of the preceding AE and the start date of the consecutive AE

For occurrence, the presence of at least one SAE /SAE suspected to be related to study treatment / non-SAE has to be checked in a block e.g., among AE's in a  $\leq 1$  day gap block, if at least one SAE is occurring, then one occurrence is calculated for that SAE.

The number of deaths resulting from SAEs suspected to be related to study treatment and SAEs irrespective of study treatment relationship will be provided by SOC and PT.

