Study Population: This study is composed of two parts: Part 1 and Part 2. Part 1 of the protocol will selectively enrol subjects with GA who have either a CFI rare variant genotype associated with low serum CFI, or with a previously unreported CFI rare variant genotype that have tested to have low serum CFI. Part 2 of the protocol will enrol subjects with GA across a broad, non-selective genetic background, irrespective of genotype, until approximately 202 subjects are randomised in the study overall.

**Rare Variant Genetic Population (Part 1):** Additional studies have found that rare genetic variants in CFI (defined by a minor allele frequency <1%) are associated with increased risk of advanced AMD, with one study showing that low serum CFI levels together with the presence of rare CFI variants is associated with an increased risk of development of advanced AMD [Seddon 2013, Kavanagh 2015, Geerlings 2017].

As CFI serves as a global down-regulator of the alternative pathway [Lachmann 2016], an increase in intraocular CFI level has the potential to dampen an over-activated complement system associated with AMD, reducing the progression of the disease.

CFI rare variant genotypes previously associated with low serum CFI or subjects carrying an unreported CFI rare variant genotype that have tested to have a low serum CFI for study entry.

Part 1 of the study will close for enrolment once all appropriate approvals for protocol V6.0 are in place; subsequently, subjects with GA and a CFI rare variant genotype should then be entered into Part 2 of the study.

**Broad Genetic Population (Part 2):** Overactivation of the complement system is also implicated in the risk of disease development across the broader dry AMD population, as shown by significant enrichment of common genetic risk factors mapping to complement proteins involved in the alternative pathway e.g. complement factor H (CFH), CFI, complement factor B (CFB), and complement component 3 (C3) [Fritsche 2013; Fritsche 2016].

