## 1 Introduction

The EXPLORE study (CPPY988A12202) is being terminated early as Novartis has made the decision to stop the current clinical development program for GT005 in subjects with geographic atrophy based on the results from the futility interim analysis. All GT005-treated subjects will be transferred into the long-term safety follow-up study, ORACLE (CPPY988A12203B).

The purpose of this Statistical Analysis Plan (SAP) is to describe the implementation of the statistical analysis planned in/changed from the study protocol, and to provide detailed statistical methods that will be used for the EXPLORE Clinical Study Report (CSR).

A final analysis will be conducted once all enrolled subjects complete (or discontinue prior to) the Week 96 visit and final Database Lock (DBL) is achieved. Data will be analyzed according to the data analysis plan described in this document that will be incorporated into the CSR.

This SAP is based on the EXPLORE Clinical Study Protocol V6.0, dated 6 December 2022.

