### 2.6.1 Secondary endpoint(s)

The corresponding secondary endpoints are:

1. Change from baseline through Week 96 in GA area as measured by FAF
2. Frequency of treatment emergent adverse event (AE) through Week 96
3. Change in retinal morphology on multimodal imaging through Week 96
- 4.a Change in best corrected visual acuity (BCVA) Score via the early treatment for diabetic retinopathy (ETDRS) chart through Week 96
- 4.b Change in low luminance difference (LLD) via the ETDRS chart through Week 96
- 5.a Change in reading performance as assessed by Minnesota low-vision reading test (MNRead) chart through Week 96
- 5.b Change in functional reading independence (FRI) index through Week 96
6. Change in quality of life measured on the visual function questionnaire-25 (VFQ-25) through Week 96

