### **2.7.1.1 Adverse events of special interest / grouping of AEs**

An AESI (serious or non-serious) is one of scientific and medical concern specific to the Sponsor's product or program, for which ongoing monitoring and rapid communication by the Investigator to the Sponsor can be appropriate. AESIs should also be assessed as to whether it fits the criteria of an SAE and reported appropriately. AESI should be reported as per reporting requirements [Protocol Section 8.3].

The number and percentage of subjects with AESIs will be summarized separated for ocular (study eye and fellow eye) events by category, PT, and treatment groups. In addition, AESIs related to the study treatment and/or surgical procedure will be summarized by category, PT and treatment groups.

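### After early termination, crude AE percentages to each subject's end of study could make equal AE rates look like excess harm at the high dose, which was given only in Part 1

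*SAP*

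**What the plan says.** SAP 2.7.1 sets the counting period: "Only AEs that occurred during the study period (from the date of randomization to the end of study) will be summarized". The measure follows: "The number (and percentage) of subjects with AEs will be summarized separately for ocular (study eye and fellow eye) and non-ocular events by treatment group". SAP 2.7.1.1 treats events of special interest the same way: "The number and percentage of subjects with AESIs will be summarized". For the registry tables, SAP 2.7.1 also counts occurrences of the same term, where "more than one occurrence will be counted if there is" a gap of more than one day. Those counts have no subject-time denominator either.

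The three groups (SAP 2.1.1.1) are pooled over Parts, and SAP 2.2.1 and 4 declare subgroups not applicable. SAP 2.1.1.3 makes end of study the date on which each subject completes or discontinues. In the visible text of SAP 2.7 there is no exposure-adjusted rate, time-to-event summary, common cut-off or table of follow-up time.

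SAP 1 says that the study "is being terminated early as Novartis has made the decision to stop the current clinical development program for GT005", and that "All GT005-treated subjects will be transferred into the long-term safety follow-up study, ORACLE (CPPY988A12203B". On enrolment, the Protocol Synopsis says: "Part 1 of the study will close for enrolment once all appropriate approvals for protocol V6.0 are in place". Part 2 randomises to low dose or untreated control only (SAP 1.1; Protocol 3.4.2). The safety secondary endpoint in SAP 2.6.1 is "Frequency of treatment emergent adverse event (AE) through Week 96".

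**The concern.** A crude percentage to end of study is a fair comparison when every arm is followed for the planned 96 weeks. Early termination removes that condition, because follow-up then depends on when a subject enrolled. Enrolment date is tied to treatment here: high-dose subjects come only from the earlier Part, while low dose and control mix earlier and later subjects. An arm watched for longer accumulates more subjects with at least one event, even if the event rate is the same everywhere.

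These tables address a secondary objective and go into the clinical study report. A reader could take a difference produced by follow-up length for a dose-related safety signal. SAP 2.5.2 and 2.6.2 adapt the efficacy analyses to early termination, subject to data availability. Section 2.7 has no corresponding change for unequal follow-up.

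**Working it through.** The documents state no AE rate and no follow-up by arm, so there is no figure of the plan's own to reproduce on this point. What follows is a calendar check and an illustration under stated assumptions.

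**Inputs from the documents.** Protocol V6.0 is dated 6 December 2022 (SAP 1) and the SAP 24 January 2024 (SAP Document History). About 10 subjects were already randomised to the high dose, out of about 202 planned (Protocol 9.1; SAP 3). Allocation is 2:1 GT005 to control for each dose group, which implies about 1:1:1 high, low and pooled control in Part 1. Part 2 is 2:1 low dose to control. Planned follow-up is 96 weeks.

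**Calendar.** 6 December 2022 to 24 January 2024 is 414 days, and 414/7 = 59.1 weeks. At the SAP date no Part 2 subject could have more than about 59 weeks. The high-dose subjects already randomised when V6.0 was written had potential follow-up of at least 59 weeks, up to 96.

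**Illustration 1: equal hazards, a range of Part 2 sizes.** Assumptions: Part 1 has 10 per arm, followed either 96 weeks or uniformly 59–96 weeks. Part 2 follow-up is uniform from 0 to a maximum of 20, 40 or 59 weeks. Every arm has the same constant hazard h, set to give 30% risk at 96 weeks: h = −ln(0.7)/96 per week. The crude percentage is the average of 1 − exp(−h·t) over the arm's follow-up times. The planned Part 2 size is 202 − 30 = 172.

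| Part 2 enrolled | Mean follow-up in weeks, high / low / control | Crude %, high / low / control |
|---|---|---|
| 172 | 78–96 / 15–35 / 20–39 | 25–30 / 5–12 / 7–13 |
| 60 | 78–96 / 24–43 / 32–52 | 25–30 / 8–14 / 11–17 |
| 15 | 78–96 / 44–63 / 55–74 | 25–30 / 14–20 / 18–23 |
| 0 | 78–96 in each arm | 25–30 in each arm |

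**Illustration 2: what kind of adjustment works.** Assume 10 per arm in Part 1 followed 96 weeks, 60 in Part 2 (40 low, 20 control) followed 30 weeks, and a hazard of 0.5 per year in every arm.

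- Part 1 risk: 1 − exp(−0.5 × 96/52) = 60.3%. Part 2 risk: 1 − exp(−0.5 × 30/52) = 25.1%.
- Crude: high 60%; low (10 × 60.3 + 40 × 25.1)/50 = 32%; control (10 × 60.3 + 20 × 25.1)/30 = 37%.
- Mean follow-up: high 96 weeks; low (960 + 1200)/50 = 43.2; control (960 + 600)/30 = 52.
- Subjects with an event divided by total time to end of study, per 100 subject-years: 32.6 high, 38.6 low, 36.8 control. The bias is now reversed.
- Time at risk ended at first event: expected time is (risk)/h, so the rate is 50 per 100 subject-years in all three arms.

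**Events around surgery.** Suppose 50% of subjects in each dose arm have an event at surgery and none later. Over total follow-up the rates are 50/(96/52) = 27 and 50/(43.2/52) = 60 per 100 subject-years, high and low. Ending time at first event does not help, since only the event-free half contributes time: 54 and 120. Such events need a fixed early window.

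**Opposite direction: ORACLE.** If transfer ended high-dose follow-up at 59, 72 or 80 weeks while controls stayed to Week 96, the same 30% event would show as 19.7%, 23.5% or 25.7% at the high dose against 30% in control.

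**The case against.** The strongest reply is that the follow-up gap is inferred. The documents give no number randomised in Part 2, no termination or transfer date, and no statement of when controls end the study. The 59 weeks runs to the SAP date, which precedes final lock. Part 1 stayed open until V6.0 approvals were in place, so late high-dose subjects may be truncated too. All of this stands, and is why the size is given as a range that includes zero.

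The reply also has force on precision and timing. With about 10 high-dose subjects, each is 10 percentage points, and 3 of 10 has an exact 95% interval of 7–65%. Protocol 9.4.2 plans no inferential testing. Surgical events cluster early and depend little on late follow-up, and SAP 2.7.1 tabulates procedure-related events separately. SAP 2.3.1 lists early discontinuations with the last visit completed. These points limit how much weight the tables can bear, but none removes the bias from the summaries of events that accrue over time.

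A reader might infer that transfer to ORACLE is what makes the high dose look worse. The documents do not support that: transfer covers both doses and no controls, so alone it would shorten GT005 follow-up and hide harm. A reader might also infer a material advantage for low dose over control. In Illustration 2 that gap is 32% against 37%, and in Illustration 1 it is under 5 points throughout.

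**Conclusion.** The point holds in a conditional form. Following SAP 2.7.1 and 2.7.1.1 as written, equal AE rates could look like excess harm at the high dose, because that arm comes only from the earlier Part. For an AE with 30% risk at 96 weeks, under equal constant hazards and with 15 to 172 subjects in Part 2, the spurious excess is about 7 to 24 percentage points over low dose and 5 to 22 over control. It is nil if Part 2 enrolled nobody. These figures rest on 10 subjects per arm in Part 1 and on the assumed follow-up distributions.

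The documents do not show that follow-up actually differs greatly, or that a false signal will appear. Differential transfer to ORACLE is a separate risk in the opposite direction for GT005 against control. That the bias could run either way is itself a reason to report follow-up and to adjust for it. This is a worthwhile, inexpensive improvement to a descriptive safety analysis.

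**What to change.** Amend SAP 2.7.1, and 2.7.1.1 to match:

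1. Summarise follow-up time from randomisation to end of study by treatment group and Part.
2. For the main TEAE, SAE and AESI summaries, add exposure-adjusted incidence per 100 subject-years, with time at risk from randomisation to first event or end of study, whichever is earlier. A Kaplan-Meier cumulative incidence would serve instead. Do not divide subjects with an event by total follow-up.
3. Repeat the main study-eye and SAE tables for a common early window, for example randomisation to Week 24, with the numbers still followed. Use that window for events around surgery.
4. Show the high dose against Part 1 low dose and Part 1 control.

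Keep the crude tables for registry posting, but do not base between-arm statements on them alone. If the database is already locked, add these as tables labelled as additional in the study report.

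The cost is SAP wording and a few descriptive tables from dates already collected. With about 10 high-dose subjects the estimates will be imprecise, and constant-rate summaries fit perioperative events poorly, which is why item 3 is needed alongside item 2.
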